#### 5.2 Planned trial interventions

The intervention group will receive intravenous tenecteplase as a single bolus at a dose of 0.25 mg/kg body weight (maximum dose 25 mg) as soon as possible after randomization.

The control group will receive standard of care dosing of intravenous alteplase (0.9 mg/kg body weight, 10% bolus and 90% infusion as per standard care, maximum dose 90 mg).

All patients will have standard of care medical management on an acute stroke unit. There are no additional trial specific management recommendations.

#### 5.2.1 Study Drugs

Intravenous tenecteplase: The trade name for tenecteplase is TNKaseTM in Canada.

TNKaseTM is available as 50mg vials. Each 50mg vial of TNKaseTM is packaged with one 10ml vial of sterile water for injection for reconstitution. Reconstitution of 50mg of tenecteplase in 10 ml of sterile water results in a solution concentration of 5mg/ml.

Intravenous alteplase: The trade name for alteplase is ACTIVASETM in Canada. This thrombolytic agent is the current standard care.

ACTIVASE™ is reconstituted by aseptically adding to the vial the appropriate volume of sterile Water for Injection, (100 mL for 100 mg vials) resulting in a solution concentration of 1mg/ml.

#### 5.2.1.1. Drug Labelling

The trial is testing a standard, off-the-shelf drug (alteplase) vs. another off-the-shelf drug (tenecteplase) currently used for another indication i.e. acute myocardial infarction. The drug packages describe the expiration date of the drug, the recommended storage conditions, the drug reconstitution method and the LOT number. An Investigational Status Assessment (ISA) has been completed for use of alteplase; therefore, no labeling is required for alteplase drug packages. The sponsor will provide labels and the site PI will ensure that the tenecteplase drug packages are labelled as investigational with the current protocol version. The labels will also have the drug dosage as per current protocol and the name and address of the sponsor (See Appendix for Drug labels). To facilitate labelling and integration with clinical workflow, the sponsor can help sites make a "stroke kit" available, stocked with labelled tenecteplase and alteplase In addition, copies of the mixing and dosing chart can be made available to sites as posters. Finally, the randomizer (text or web based) will also provide instructions on mixing and dosing.

#### 5.2.1.2 Drug Traceability

Sites will be collecting LOT numbers and expiry date of the vial of drug administered to a patient and entering these numbers into the study database by study ID number. Pharmacy Drug Recall records are able to track LOT Numbers, expiry, vendor and patient name using a logic match.

#### 5.2.1.3 Drug Storage/Temperature Monitoring

Both drugs are kept in environmentally controlled conditions i.e. a hospital, by hospital pharmacies, according to the information on the current drug labels, and made available for use as required. The current label on storage requirement for tenecteplase mentions that the drug may be stored at room temperature not to exceed 30°C. Environmentally controlled conditions in the participating hospitals ensure such storage conditions for current clinical use of tenecteplase.

#### 5.2.2. Clinical and Imaging Evaluations

There are no trial specific clinical and imaging evaluations except as per standard care. 90-120 day outcome using the modified Rankin Scale and EQ-5D-5L will be collected by the trial in coordination with the site. All other data will be collected either through the QuICR and OPTIMISE registries or through administrative data linkages. (See sections 5.11, 7.4 and Appendix)

#### 5.2.3 Laboratory Evaluations

There are no trial specific laboratory evaluations and no central laboratory. All laboratory evaluations are as per standard care only.

#### **5.2.4** Concomitant medications

Standards of care applicable to any patient receiving intravenous alteplase apply to patients in both arms of the trial. There are no prohibited medications except those considered as such based on best practices.

#### 5.3 Proposed practical arrangements for allocating participants to trial groups

Eligible patients will be randomized in a 1:1 ratio. Randomization will use a validated minimal sufficient balance (MSB) algorithm, to assure balance by site. The algorithm will kick in after the site has enrolled 5 subjects. The standard distribution is 50-50, but when an imbalance is detected with a p-value less than 0.3, the distribution changes to 65-35 in the direction against the imbalance. Randomization will be centralized, secure and concealed using a real-time web-based server, thus eliminating the possibility of confounding due to allocation bias. The central server will be linked to a randomization mechanism and will only be able to allocate one patient to either arm of the trial at one time. Investigators will be able to rapidly access the randomizer through a secure internet web browser or secure automated phone number or text message. Investigators will have to enter a site-specific ID number followed by an Investigator specific ID number and the weight of the patient in kilograms. They will then receive the drug allocation (tenecteplase vs. alteplase) along with unique study subject ID and the calculated drug dosage. They will later be prompted to enter if a) the correct drug was administered b) the correct dose was administered and c) the vial LOT number and expiry date of the administered drug.

Emails will be sent from the central trial server to site investigators and trial personnel with the site ID, unique study subject ID and drug allocation (study enrolment form). A copy of this email can be

printed and included in the patient chart. In addition, this email will also have a PDF checklist reminding site co-ordinators to ensure the following

- 1. The study enrolment form is placed in the clinical patient chart
- 2. The patient and surrogate contact information is documented in the checklist
- 3. Consent is obtained (see section 5.4) and documented in the study database
- 4. The unique study subject ID and registry ID are entered in the study database
- 5. Report any serious adverse events occurring within the first 24 hours of randomization. This information will be documented on paper and/or in the study database

Each site will maintain a patient log that will include the above checklist, a copy of the patient enrolment form and patient or surrogate consent forms (if not obtained electronically; see section 5.4 Consent). The central trial coordinator and/or the automated study database application will contact the site registry coordinator within 7-10 days of enrolment to ensure the above steps are complete. A manual of procedures (MOP) will be made available to each participating site detailing all the steps above.

#### 5.4 Consent

Where approved by the local research ethics board (REB), to reduce time to treatment, patients will be randomized using a deferral of consent procedure. The responsible treating physician will determine patient eligibility for the trial and initiate randomization if the patient is deemed eligible for the trial.

All patients will be enrolled by deferred consent. This study design respects TCPS2 guidelines and reflects the imperative to treat patients quickly, so as not to bias results or disadvantage enrolled patients compared to patients not enrolled in the trial. Because of this design, we will institute the following patient protections: 1. Identify a specific ethics lead ([name], a stroke neurologist and ethics researcher from the University of Ottawa), a patient engagement expert ([name], Alberta Health Services) and a patient/caregiver lead; 2. Develop a patient-oriented, 1-page information sheet for patients and their families at the time of enrollment (the information sheet); 3. Develop a patient-oriented, 2-page consent form for patients and their families regarding ongoing participation in the trial; 4. Develop a questionnaire to be administered to a sample of enrolled patients about their experiences with and attitudes towards deferred consent; 5. Hold a focus group with stroke patients to review the trial protocol and above documents prior to initiation of the trial. Past precedence with the ESCAPE trial (Shamy MCF et al; Deferral of Consent in Acute Stroke Trials: Lessons from the ESCAPE Trial. Stroke 2019; in press) suggest that deferral of consent is practical at all sites.

A detailed document outlining justification for deferred consent based on the Declaration of Helsinki Article 26 and Article 3.8 of the Tri-council Policy Statement-2 is available for enrolling sites. It is recommended that consent be obtained from subjects or their surrogates within 7 days of randomization or before discharge, whichever is earlier. In patients who die, and consent has yet to be obtained, reasonable efforts should be made to obtain consent from their surrogates. If consent could not be obtained in spite of best efforts (no surrogate or surrogate cannot be contacted), the patient will continue

in the trial. Subjects or, if incapacitated, their legal representatives, will have the right to withdraw from further participation (including long-term follow-up by record linkage). Subjects may withdraw consent for further contact but continue follow-up via record linkage. In the event that consent is withdrawn, data collected up until the point of withdrawal will be used for analysis.

We will provide an option for a site-specific electronic consent application with electronic signature support that will be linked to the randomization tool. This solution shall be made available via a secure web-application. Alternatively, sites can print the consent form from the site and upload a scanned signed paper version. The deferred consent capture process shall consist of the following steps:

- 1) An electronic or paper physician script will be made available to the physician prior to enrolling a patient in the trial. This script will contain information that the physician can use as guideline to help inform the patient/shared decision maker (SDM) about the trial. The use of this physician script is not mandatory;
- 2) An electronic or paper information sheet will also be made available to the physician to help him/her inform the patient or shared decision maker (SDM) about the trial.
- 3) If and when the patient is capable of communicating and/or the SDM is available, the physician will provide them with the information in the sheet above. It is recognized that sharing of the information sheet with patient/SDM may happen before, during or after randomization;
- 4) After randomization has been completed for a patient, a unique identifier (study ID) will be assigned to each patient by the application, shown on-screen to the physician or site-coordinator and sent via e-mail to the site co-ordinator;
- 5) After treatment has been administered, as an added quality assurance step, a randomization validation process will be initiated. This process will confirm whether the drug and dosage used match the randomization values and, if the trial information sheet was shown to the patient and/or SDM;
- 6) Once the randomization process has been completed, in conjunction with the validation exercise, the site co-ordinator shall connect to the electronic consent capture application via a PC, tablet, or web-enabled mobile phone;
- 7) The site co-ordinator will be asked to provide the unique patient identifier and their own user identifier; additionally, the site co-ordinator will select whether consent will be provided by the patient or a surrogate, and whether electronic or paper-based consent will be provided;
- 8) The system will check to ensure the validity of the identifiers and then will show the relevant (site-specific) consent information to the participant;
  - a. If electronic consent was selected, the participant will then be asked to review the information and, if they consent, validate/check the acknowledgement box, enter their name, date, month and year of birth, signature, and submit the form.
    - i. The date of birth option can be disabled, if required/request by the REB review process
  - b. As a secondary consent capture method, the patient may choose to instead use a paper form, email or phone consent as approved by local ethics boards. If a patient chooses this option, the qualified site personnel will present the patient with a paper form with the same information as the electronic one. Once the patient fills-out this form, they will then enter the patient's unique consent id and then scan and upload the form to the electronic consent application. Either consent method shall be deemed to sufficiently satisfy the consent requirements.

- 9) Once submitted, the application will securely store the consent information and associated signature in a secure database and file store.
- 10) This information can then be reviewed by auditors or authorized personnel by requesting it of the Clinical Research Unit.
- 11) If subjects or, if incapacitated, their legal representatives, withdraw from further participation (including long-term follow-up by record linkage), sites will inform the sponsor about this within 7 days of this happening. Subjects may withdraw consent for further contact but continue follow-up via record linkage. In the event that consent is withdrawn, data collected up until the point of withdrawal will be used for analysis. The site will update the patient consent log and inform the sponsor of the same.

The policies and procedures will receive prior review and approval by the IRB/REB of all hospitals to which prospective trial subjects may be admitted. These IRB/REBs will provide ongoing oversight of the trial.

During the conduct of the trial, a publicly accessible website will be available to provide information about the trial; and after the trial's completion, the community will be notified of its outcome. The trial is also registered at www.clinicaltrials.gov.

#### 5.5 Proposed methods for protecting against sources of bias

The trial will have allocation concealment and blinded endpoint assessment. Given the time sensitive nature of acute stroke treatment, blinding the enrolling health personnel and patient to treatment allocation is not practical. Primary clinical outcome data (assessed using the modified Rankin Scale) will be determined by the Rankin Focused Assessment (RFA) method using centralized telephone interviews conducted by central trial personnel blinded to treatment allocation. The trial coordinator may contact the site to help schedule phone follow-ups. Follow-ups will be scheduled 90 to 120 days after randomization. The manual of procedures (MOP) will describe in detail the Rankin Focused Assessment method for use by central trial personnel.

#### 5.6 Inclusion/exclusion criteria

The proposed trial will recruit patients from the emergency departments of the hospitals participating in the QuICR and OPTIMISE registries.

#### Inclusion Criteria

Inclusion criteria is pragmatic. All patients with acute ischemic stroke eligible to receive intravenous alteplase as per standard care will be eligible for enrolment in the proposed trial. Patients eligible for endovascular thrombectomy in addition to intravenous thrombolysis are eligible for enrolment.

#### Exclusion Criteria

Contra-indications to intravenous thrombolysis as used by treating physicians as current standard of care apply.

The benefits of thrombolysis with intravenous alteplase in the pediatric population is unknown. Any patient < 18 years of age may therefore not be enrolled.

Women with pregnancy known to the investigator by history or examination, without requiring pregnancy testing, may only be enrolled in consultation with an expert stroke physician (either in person or through tele-stroke)

#### 5.7 Proposed duration of treatment period

All eligible patients will receive the allocated intravenous thrombolytic therapy (tenecteplase or alteplase) acutely as a one-time treatment. Intravenous tenecteplase is administered as a single bolus injection over 5 to 10 seconds while intravenous alteplase is administered as a bolus over 1 minute followed by an infusion over approximately 60 minutes. There are no additional planned co-interventions throughout the duration of the trial.

#### 5.8 Proposed frequency and duration of follow up

Duration of follow-up will be 90 days, up to 120 days. The primary outcome (mRS) will be collected at the end of follow-up (ideally at 90 days but definitely within 120 days).

#### 5.9 Primary and secondary outcome measures

#### Primary Outcome: modified Rankin Scale 0-1 at 90 - 120 days

#### **Secondary Outcomes:**

- 1. Discharge destination (home, early supported discharge, rehabilitation facility, long term care, death) \* #
- 2. Home time (defined as number of days subject spends at home after index stroke event) 
- 3. Actual 90-120 day mRS score\*#
- 4. Door to needle time\*#
- 5. Door-in-door-out (DIDO) times at Primary Stroke Centres\*#
- 6. Recanalization status (mTICI score) at first angiographic acquisition in patients taken to the angio-suite for the purpose of administering EVT\*#
- 7. Proportion of patients administered EVT \*#
- 8. Door-to-groin puncture time in patients undergoing EVT\*#
- 9. CT-to-puncture time in patients undergoing EVT\*#
- 10. Return to baseline level of functioning
- 11. Cognition assessed via a brief, on-line cognitive assessment tool.

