The ATTEST trial was a single-center phase II trial that randomized 104 patients to receive intravenous tenecteplase (0.25 mg/kg body weight) vs. standard dose intravenous alteplase. The primary outcome was the proportion of penumbra salvaged (CT perfusion-defined penumbra volume at baseline minus CT infarct volume at 24–48 h). Despite prognostic imbalances at baseline with more negative imaging features in the tenecteplase group (a higher proportion of patients with large artery occlusion 75% vs. 61% and 33% larger ischemic core volume), there were trends towards earlier major neurological improvement and lower risk of intracranial hemorrhage in patients treated with tenecteplase.

The EXTEND-IA tNK trial (published in early 2018) was another phase II trial with an explanatory framework that enrolled 202 patients with CT-perfusion mismatch and proximal anterior circulation occlusions to receive intravenous tenecteplase (0.25 mg/kg body weight) vs. standard dose intravenous alteplase before being administered standard of care endovascular thrombectomy. The primary outcome (reperfusion of greater than 50% of the ischemic territory or an absence of retrievable thrombus assessed on initial catheter angiopathy assessment before endovascular thrombectomy) occurred in 22% of patients receiving intravenous tenecteplase compared to 10% of patients receiving standard dose intravenous alteplase (rate ratio 2.2; 95% CI, 1.1 to 4.4; P=0.002 for noninferiority, p=0.03 for superiority). In secondary analysis, patients receiving intravenous tenecteplase fared better clinically compared to patients receiving alteplase (median mRS 2 vs. 3, respectively at 90 days, common odds ratio, 1.7; 95% CI, 1.0 to 2.8; p=0.04). The rate of symptomatic intracranial hemorrhage was 1% in both groups. The trial results suggest that by achieving higher earlier recanalization rates, intravenous tenecteplase is potentially capable of achieving better clinical outcomes in patients who are otherwise candidates for endovascular thrombectomy.

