#### 4.6 How will the results of this trial be used?

Results from the proposed trial are likely to provide real life confirmatory evidence about the efficacy of intravenous tenecteplase in patients with acute ischemic stroke eligible for intravenous thrombolysis as per current guidelines. If the

proposed trial demonstrates non-inferiority of intravenous tenecteplase when compared to alteplase, it

is likely to change clinical practice. Given relative ease of administration of tenecteplase (bolus only) vs. alteplase (bolus + infusion), workflow metrics in acute stroke like door-in-door-out (DIDO) time, door to needle (DTN) and door to reperfusion time can all potentially improve, thus improving clinical outcomes. In addition, better reperfusion rates and potentially better safety data is likely to increase utilization of thrombolytic therapy overall while at the same time potentially decreasing the need for resource intensive endovascular thrombectomy in many patients.

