## 7.8 Ancillary Studies, Co-Enrollment and Publication Policy

The trial steering committee will constitute a publication committee that will include site principal investigators and the lead statistician. Policies will be detailed in a Publication Policy Charter. Ancillary studies will also be vetted by the trial steering committee and a decision made on merits of the proposed study.

Patients enrolled in the AcT RRCT are eligible to be enrolled into the EASI-TOC RCT. This study targets a subgroup of patients with ischemic stroke who have what are called tandem occlusions. EASI-TOC aims to determine whether, in addition to thrombectomy to recanalize intracranial occlusion (standard of care); patients with a tandem occlusion should also be acutely treated with a stent to revascularize their cervical internal carotid artery during the thrombectomy procedure. Inclusion in the AcT and EASI-TOC trials do not subject patients to increased risk. No multiplicative biological interaction between the interventions studied in both studies is expected. Patients are randomized just before or at the start of the thrombectomy procedure, once the carotid lesion is

confirmed by angiography. The allocation is 1:1 (stent versus no stent). Both approaches lesion is confirmed by angiography. The allocation is 1:1 (stent versus no stent). Both approaches used in EASI-TOC are considered standard care and used in daily clinical practice. Neither approach is therefore experimental. The pragmatic design of the two studies prevents patients from being subjected to additional study specific investigations, procedures or clinical follow-up beyond usual care.

It is estimated that < 5% of patients eligible for enrolment into the AcT RRCT will also be candidates for EASI-TOC (approximately 60-80 patients out of a planned 1600 patients to be included in AcT). Approximately 1/3rd of subjects eligible for AcT will likely undergo endovascular thrombectomy i.e. 533 subjects.

Statistical simulations with different possible interaction scenarios suggest limited effect on outcomes within both studies. Outcome ascertainment in EASI-TOC does not influence or affect outcome ascertainment in AcT. There are precedents in medicine for including patients in more than one randomized trial, especially in the fields of oncology and critical care and more recently with COVID-19.

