#### **10. Subgroup Analyses**

Heterogeneity in treatment effects will be explored via subgroup analyses of pre-specified prognostic variables in the ITT population primarily and in the per-protocol population secondarily. These will include analysis of primary outcome (mRS01) and key safety outcomes by

- a. age (continuous and as < 80 years vs. >= 80 years),
- b. sex (male vs. female),
- baseline stroke severity as measured by the National Institute of Health Stroke Scale (NIHSS; continuous and < 8, 8-15 vs > 15),
- d. presence of large vessel occlusion on baseline CTA
- e. stroke onset-to-needle time (continuous and as <=180 minutes vs. > 180 minutes)
- f. registry (QuiCR vs. OPTIMISE),
- g. type of enrolling hospital (PSCs vs. CSCs),

Evidence of a treatment-by-sub-group variable interaction will be tested by including a multiplicative interaction term (treatment\*subgroup variable) in the model. Subgroup analyses will help to determine if there is efficacy or futility in any pre-specified subgroup. Statistical significance for each subgroup analysis will be exploratory and conducted at  $\alpha = 0.05$ 

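### Recanalization and puncture-time outcomes are compared in a subset formed after open-label treatment, so randomisation does not protect those between-arm tests

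*Combined protocol and SAP*

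**What the plan says.** Protocol 5.9 lists four secondary outcomes that bear on this point.

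- Item 6: "Recanalization status (mTICI score) at first angiographic acquisition in patients taken to the angio-suite for the purpose of administering EVT".
- Item 7: "Proportion of patients administered EVT", with no subset stated.
- Item 8: "Door-to-groin puncture time in patients undergoing EVT".
- Item 9: "CT-to-puncture time in patients undergoing EVT".

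Protocol 4.6, on how results will be used, names better reperfusion and "potentially decreasing the need for resource intensive endovascular thrombectomy in many patients" as possible benefits of tenecteplase.

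Protocol 6.6 assigns logistic regression to binary secondary outcomes, and ANCOVA and mixed-effects regression to continuous ones. If non-inferiority is shown, a hierarchical procedure controls the familywise error across secondary outcomes. It makes no exception for outcomes measured in a subset.

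The SAP outcome table (section 9) gives the EVT proportion a risk difference, a 95% confidence interval and an adjusted model. It has no row for mTICI or for either puncture time. SAP section 10 lists "presence of large vessel occlusion on baseline CTA" as a subgroup variable.

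**The concern.** Items 6, 8 and 9 condition on reaching the angio-suite or undergoing EVT. Both happen after randomisation and after the study drug, in an open-label trial where those deciding on angiography may know the allocation. The protocol says the drug may change how many patients need EVT, and it makes the EVT rate an outcome. If the drug alters who enters the denominator, the two remaining groups are no longer randomised groups, and a difference between them mixes drug effect with selection.

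For mTICI there is a specific mechanism. A patient whose vessel opens early enough that the trip is called off is a success of the drug but does not appear in the outcome. For puncture times no success is being scored. There the concern is simply that the patients compared may differ.

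Early reperfusion is one of the protocol's stated reasons for the trial (4.3, 4.6). A formal test of it should compare groups that randomisation made comparable.

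**Working it through.** **Plan's own figure.** The documents give no sample size or power for items 6, 8 or 9. The only stated calculation is for the primary outcome: 759 per arm. With unpooled variance, (1.960 + 1.282)² × (0.35×0.65 + 0.38×0.62) / 0.08² = 10.507 × 0.4631 / 0.0064 = 760.3, so 761 per arm. The plan's figure reproduces, 2 × 759 / 0.95 = 1598 agrees with 1600, and this point does not touch it.

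**Inputs for an illustration of item 6.**
- Early reperfusion r: in the phase II trial described in Protocol 4.3.4, the outcome "occurred in 22% of patients receiving intravenous tenecteplase compared to 10% of patients receiving standard dose intravenous alteplase".
- Number of patients: Protocol 7.8 says "Approximately 1/3rd of subjects eligible for AcT will likely undergo endovascular thrombectomy i.e. 533 subjects". That is 266.5 per arm.
- Share s of early reperfusers who never reach the angio-suite: not in the documents, so a range is shown.

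Neither documented input fits exactly. The 533 are patients expected to undergo EVT, so they are already past the filter; here they stand in for patients with an occlusion. The 22% and 10% were read on the initial catheter angiogram; here they stand in for rates before any loss. Section 5.9 gives no mTICI cut-off, so the outcome is treated as yes/no.

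**Equal loss in both arms.** The observed rate is r(1−s)/(1−rs), among 266.5(1−rs) patients per arm. Power is Φ((d − 1.96·SE₀)/SE₁), with SE₀ pooled and SE₁ unpooled, two-sided 5%.

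| s | Tenecteplase | Alteplase | Difference (points) | Risk ratio | Odds ratio | Power |
|---|---|---|---|---|---|---|
| 0 | 22.0% | 10.0% | 12.0 | 2.20 | 2.54 | 97% |
| 0.25 | 17.5% | 7.7% | 9.8 | 2.27 | 2.54 | 92% |
| 0.50 | 12.4% | 5.3% | 7.1 | 2.35 | 2.54 | 80% |
| 0.75 | 6.6% | 2.7% | 3.9 | 2.44 | 2.54 | 52% |

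At s = 0.50 the lost successes are 0.50 × 0.22 × 266.5 = 29 on tenecteplase and 0.50 × 0.10 × 266.5 = 13 on alteplase.

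The odds ratio is constant because the observed odds are r(1−s)/(1−r). The factor (1−s) cancels between arms, leaving (0.22/0.78)/(0.10/0.90) = 2.54.

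**Unequal loss.** The odds ratio becomes 2.54 × (1−s_T)/(1−s_A), where s_T and s_A are the shares lost on tenecteplase and alteplase.
- s_T = 0.50, s_A = 0.25: 12.4% vs 7.7%, odds ratio 1.69.
- s_A = 0.25: the arms are equal at s_T = 1 − 0.75/2.54 ≈ 0.70.
- s_T = 0.75, s_A = 0.25: 6.6% vs 7.7%, odds ratio 0.85, a reversal.
- s_T = 0.25, s_A = 0.50: 17.5% vs 5.3%, odds ratio 3.81, an exaggeration.

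**Puncture times.** The documents contain nothing from which to compute a size or a direction.

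**The case against.** Several points on the other side are sound.

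- A reader might infer that a drug which opens vessels early loses all its successes from the comparison. It does not. Item 6 is read in patients taken for EVT whether or not EVT follows, so a vessel already open at that moment counts. Only recanalization that prevents the trip is lost.
- A reader might also infer that the outcome must shrink a real effect. On the odds-ratio scale, which is the scale of the logistic regression in Protocol 6.6, equal loss leaves the effect unchanged, and the risk ratio rises. Bias on the odds-ratio scale needs unequal loss.
- The inputs to the illustration sit at or past the angiography filter, and the share lost has no source. The power figures do not describe this trial.
- The SAP analyses the EVT proportion without a subset, so a difference in entry to EVT would be visible. The SAP also calls its analyses of other registry outcomes exploratory, which is close to a descriptive label.
- Protocol 4.6 says only that the need for EVT may fall.

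These points limit the concern without removing it. The EVT proportion can reveal selection but cannot correct it, since EVT may be withheld for recanalization, deterioration or other reasons. The SAP's exploratory wording does not name mTICI or puncture times, so the general testing rule in Protocol 6.6 still applies to them. The phase II trial enrolled patients with proximal occlusion ahead of planned thrombectomy, so its denominator was set at entry. This trial enrols all patients eligible for thrombolysis.

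**Conclusion.** The point holds in limited form. Items 6, 8 and 9 are compared in groups formed after open-label treatment that the protocol says the drug may change. Randomisation does not protect those comparisons, and neither document restricts how they are tested or read.

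For mTICI, equal loss lowers the absolute difference and the power but not the odds ratio. Unequal loss can bias the result in either direction. For puncture times the patients may be non-comparable, with unknown direction. The size cannot be derived from the documents. The figures rest on an assumed share lost and on stand-in inputs, and show only how the mechanism works.

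The documents do not support reading this as a demonstrated bias against tenecteplase, or as a threat to the trial's main conclusion. The primary mRS 0-1 comparison and its sample size are unaffected.

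**What to change.** In Protocol 5.9 and the SAP:

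1. Report mTICI at the first angiogram and both puncture times by arm as descriptive results, not as between-arm tests, next to the EVT proportion.
2. Add a comparison, in all randomised patients with large vessel occlusion on baseline CTA, of EVT use and of angiographically documented early reperfusion. This denominator is fixed before treatment.
3. For reperfusion, give bounds that score patients not taken to angiography first as all failure and then as all success.
4. In the main version, do not count clinical recovery without imaging as reperfusion. In an open-label trial that would let unblinded judgement define success.

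The cost is wording and two analyses on a variable the SAP already uses. No new imaging or data field is needed. The downside is that the bounds may be wide, because patients stay out of the angio-suite for reasons unrelated to reperfusion. Scoring both arms alike also does not cover every pattern of unequal loss, so the bounds should be labelled as sensitivity analyses.
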